*** 1. Project Title:**

If this is a funded project, please use the same title as that on the funding application. This will allow for easier communication with the Sponsored Programs Office.

Promoting gastrointestinal health and reducing subclinical inflammation in obese individuals through intake of whole wheat products in comparison with fruits and vegetables - (CT.gov registered - SF)

*** 2. Principal Investigator's Status:**

Faculty

*** 4. Project Type:**

Research

*** 5. Does the research involve an outside institution/agency other than UNL?**

No

Note:

Research can only begin at each institution after the IRB receives the institutional approval letter.

*** 6. Where will participation take place (e.g., UNL, at home, in a community building, schools, hospitals, clinics, prisons, unions, etc)? Please specify and give location if not already listed above.**

UNL

*** 7. Briefly describe the facilities available for the research (e.g., there will be a quiet room in the school to conduct interviews, a secure lab space is available, etc).**

Subject screening interviews will take place in a private room on campus. During the intervention, subjects will pick up treatment foods in a classroom on campus. Stool collection will take place at the subjects' homes. Blood collection will take place at the student health center on campus.

Project Information

*** 8. Present/Proposed Funding Source:**

Agricultural Research Division

*** 9. Project Start Date:**

(Start date is dependant upon IRB approval)

01/01/2015

*** 10. Project End Date:**

08/31/2017

Description of Multi-Institutional Study Coordination

*** 11. Is this a Multi-Institutional Study?**

No

Project Information (Continued)

*** 1. Does the research involve prisoners?**

No

*** 2. Will the research only be conducted in schools or educational settings?**

No

*** 3. Does the research involve only the use of educational tests, survey procedures, interview procedures, or observation of public behavior?**

No

*** 4. Does the research involve only the collection or study of existing data, documents, records, pathological specimens, or diagnostic specimens?**

No

*** 5. Does the research involve only studying, evaluating or examining public benefit or service programs?**

No

*** 6. Does the research involve only a taste and food quality evaluation or food consumer acceptance study?**

No

**** 7. Does the research present more than minimal risk to human subjects?**

No

For each category, please mark if it is a part of the project:

- Clinical studies of drugs and/or medical devices.**
- Collection of blood samples by finger stick, heel stick, ear stick, or venipuncture.**
- Prospective collection of biological specimens for research purposes by noninvasive means.**
- Collection of data through noninvasive procedures routinely employed in clinical practice, excluding procedures involving x-rays or microwaves.**
- Research involving materials (data, documents, records, or specimens) that have been collected, or will be collected solely for non-research purposes (such as medical treatment or diagnosis).**
- Collection of data from voice, video, digital, or image recordings made for research purposes.**
- Research on individual or group characteristics or behavior (including but not limited to, research on perception, cognition, motivation, identity, language, communication, cultural beliefs or practices, and social behavior).**
- Research employing survey, interview, oral history, focus group, program evaluation, human factors evaluation, or quality assurance methodologies.**

*** 7.a. Does the research involve only procedures included in the previous 8 categories?**

No

*** 7.b. Could identification of subjects put them at risk of criminal or civil liability, or be socially or economically damaging?**

No

Description of Participants

* 1. In the chart below, please indicate the estimated number of participants per category.

	Male	Female	Unspecified	Totals
Adults			100	
Children				
Totals				

* 2. Please indicate what special groups will be utilized/recruited for your study. Check all that apply.

- Adults, Non Students**
- Language Impaired**

- | | |
|--|---|
|  UNL Students |  Persons with HIV/AIDS |
|  Children (under age 19) |  Prisoners |
|  Decisionally Impaired |  Persons with Psychological Impairment |
|  Institutionalized Persons |  Persons with Mental Retardation |
|  Students |  Adults w/ Legal Representatives |
|  Pregnant Women/Fetuses/Neonates |  Handicapped |
|  Persons with Neurological Impairment |  Employees |
|  Persons with Limited Civil Freedom |  Other |

Inclusion Criteria

*** 3. Will participants of both sexes/genders be recruited?**

Yes

*** 4. Will participation be limited to certain racial or ethnic groups?**

No

*** 5. Describe the participant population to be included in this research and how they are selected, including any special characteristics targeted for inclusion.**

120 obese men and women (body mass index, BMI, 30 kg/m²) who are free of known gastrointestinal disease, do not take supplements, participate in less than 1 h of exercise per week, have not taken antibiotics in the last six months, have a low typical intake of fruits, vegetables, and whole grains, are willing to adhere to intervention instructions (either consume 5 servings of fruits and vegetables per day or 3 servings of whole grain foods per day will), are willing to provide 2 stool samples and 2 blood samples to study personnel, and willing to complete 2 diet history questionnaires online, will be recruited from the University of Nebraska-Lincoln and the surrounding community using paper and online advertisements.

*** 6. Describe your access to the population that will allow recruitment of the necessary number of participants.**

Fliers will be placed in the unions on city and east campus and at the dairy store. These establishments are frequented by many people throughout the day. Online advertisements will also be posted to the Food Science Facebook page and departmental website.

*** 7. The research plan should have adequate provisions to protect the privacy interests of participants. Explain provisions to protect privacy interests of participants. This refers to how investigators will access private information from or about participants during and after their involvement in the research (e.g., time, place, etc of research procedures).**

Data will be stored on two computers belonging to the principal investigator and the graduate student on the project. These computers are kept in locked offices when not in use and have single users. Only 1 file will contain subjects' names and contact information. All other documents will contain only coded names of subjects. If files need to be shared among collaborating investigators, only the files containing coded names will be used.

*** 8. Describe your process to ensure that all persons assisting with the research are adequately informed about the protocol and their research-related duties and functions.**

Potential participants will meet with study personnel. Study personnel will inform subjects of all procedures and requirements. Subjects will provide written informed consent to participate.

Exclusion Criteria

*** 9. If not already described above, will any groups or categories of participants be excluded from this research?**

No

*** 10. Will some or all subjects likely be vulnerable to coercion or undue influence?**

No

Unique Research Methodology or Data Sources

*** 1. Will your project involve audio taping?**

No

*** 2. Is this project web-based research?**

Yes

*** 2.a. For web-based studies, how will the data be handled? Will the data be sent to a secure server? Will the data be encrypted while in transit? Will you be collecting IP addresses?**

Potential subjects will complete a diet history questionnaire online. Each subject will receive the log in web address (<https://riskfactor.cancer.gov/dhq2.html>) and a unique ID and password. Subjects' ID will be their 3-digit code number used for identification purposes. Subject responses will be collected using a unique web address for the research personnel only. This web address will only be available to the research personnel listed on this IRB form. This web address requires a username and password log in. The site is hosted by the National Cancer Institute. No IP addresses will be collected.

*** 3. Is this study utilizing Protected Health Information (PHI; e.g., information obtained from a hospital, clinic, or treatment facility)?**

No

*** 4. Does this project involve genetic data, sampling, or analysis?**

No

*** 5. Does this project ask questions about illegal drug use or criminal activity that places the participant at risk for legal action?**

No

*** 6. Does this project involve photography?**

No

*** 7. Does this project involve videotaping?**

No

*** 8. Does this project involve archival or secondary data analysis?**

No

*** 9. Does this project involve biological samples?**

Yes

*** 9.a. Where are you getting your samples from? What are the samples?**

All subjects will provide blood and stool samples 2 times during the study.

Blood will be collected using standard venipuncture techniques by a licensed technician at the University Health Center room 205. Blood samples will be centrifuged and the plasma will be aliquoted into multiple tubes, labeled with the subjects' 3-digit ID code and the date of collection (no name) and then snap frozen in liquid nitrogen. Plasma will be

transported back to the lab (252 FIC) on dry ice. Once samples are received in the lab, they will be stored in freezer boxes at -80 C until analysis.

Stools will be collected using a stool collection pan that fits on the toilet seat in the privacy of the subjects' homes or in the restroom at the University Health Center. Stool samples will be transferred to a specimen bag, labeled with the subjects' 3-digit ID code and the date of collection (no name) and then snap frozen in liquid nitrogen. The samples will then be handled as described for blood.

*** 10. Does this project ask participants to perform physical tasks?**

No

Research Purpose of Project

*** 1. What is the significance/purpose of the study? (Please provide a brief 1-2 paragraph explanation in lay terms, to include a brief literature justification.)**

This project will provide new evidence in support of whole wheat in the diet for prevention of inflammation and reduction of risk factors of many of the very diseases that have been implicated in wheat-based diets. This project could lead to improved understanding of how whole wheat mediates an anti-inflammatory effect, allowing health professionals to offer better suggestions to individuals on how to make the most positive impact on health through diet. Due to the rising problems associated with consumer health, this project has the potential to have a positive impact on the well-being of many individuals.

We will focus on wheat in this project for several reasons. First, this is a requirement of the funding agency. Second, our previous research suggests that the indigestible components of wheat are particularly important in butyrate, and anti-inflammatory microbial metabolite, that we hypothesize plays a role in the health benefits of whole grain diets.. Third, wheat is an important commodity in Nebraska. Research supporting wheat consumption would be beneficial for Nebraska wheat producers.

Methods and Procedures

*** 2. Describe the data collection procedures and what participants will have to do.**

During recruitment, potential subjects will complete a diet history questionnaire online as part of the screening process. This questionnaire takes about 1 h and can be filled out at any time on any computer that is connected to the internet. Subjects will also be screened in a phone or personal interview. During this interview, subjects will be inquired as to whether they meet all of the inclusion criteria or not. This includes:

-Have no known gastrointestinal diseases

-If a student, you will not graduate before Aug 2015

-Be 19 years of age or older

-Have not taken antibiotics within the last 6 months

-Participate in less than 1 hour of structured exercise per week

-Have a low typical intake of fruits, vegetables, and whole grains (this will be assessed by the diet history questionnaire and should be <1 serving/d for each food group)

Have no known allergies to fruits, vegetables, or grains

Have a body mass index above 30

Be willing to adhere to intervention instructions (either consume 5 servings of fruits and vegetables per day or 3 servings of whole grain foods per day)

Be willing to provide 2 stool samples and 2 blood samples to study personnel

Be willing to complete 2 diet history questionnaires online

Be willing to fill out a gastrointestinal symptom questionnaire weekly during the study

Be willing to keep track of consumption of test foods on a daily basis

Enrolled subjects will be required to visit the study facility 6 times (weeks -1, 0, 1, 2, 3, and 4). At the study facility visit subjects will collect and turn in diet records and GI symptom questionnaires and order and pick up food items. At weeks -1 and 3, subjects will also receive stool collection kits to turn in at the clinical facility visits (described in the next paragraph). Each study visit will take about 20 min. During this 20 min, subjects will turn in diet records and GI symptom questionnaires. They will also pick up food items ordered the previous week and order food items for the next week. They will also have a chance to speak with the study personnel about any concerns. On visits -1 and 3, subjects will also receive stool collections kits with instructions on how to use them.

Subjects will be required to visit the clinical facility 2 times (weeks 0 and 4). At the clinical facility visit, subjects will be fasted (12 h fast) and a blood sample will be taken by a licensed phlebotomist using standard venipuncture techniques. Weight and height will be recorded. Subjects will give their stool sample to the study personnel either already collected or collected at the facility. If the subjects is unable to defecate at either of these times, they will be instructed to contact the study personnel as soon as possible after the visit to have the stool sample picked up.

The food diary requires writing down all of the fruits, vegetables, and whole grain products consumed everyday. There is a form supplied to help with this. For fruits and vegetables, subjects should write down the form (whole, peeled, juice, cooked, raw, etc.) that they were consumed in addition to the amount. For whole grains, subjects should write down the type of food and brand as well as the amount consumed.

*** 3. How long will these procedures take the participants to complete? Please describe the duration of the session, the number of sessions, over what period of time, etc.**

The blood and stool collection will take 20-30 min each session. The diet history record takes about 1 hour to complete. Each subject will complete these sessions at the beginning and the end of the study. During the study, subjects will be required to incorporate 3 servings of whole grain per day; 5 servings of fruits and vegetables per day; or noting (control) into their normal diets. This will take minimal extra time.

Total estimated time for participation in this study is 6 hours over the course of 5 weeks (six 20 minute study facility visits; two 30 minute clinical facility visits; two 60 minute diet history questionnaires; 60 minutes cumulative time filling out dietary records and GI symptom questionnaires).

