**NCT02602496**

## **Statistical analysis**

Power. We estimated that we would be able to detect an effect size of 0.4 with 80% power by recruiting 52 subjects total divided into 3 groups. This was based on our whole grain barley and brown rice feeding trial in overweight subjects, where we saw an effect size of 0.48 for change in IL-6 with the whole grain treatment.

Analyses after the intervention. All data with the exception of OTU comparisons will be analyzed using SAS software (version 9.4, SAS Institute, Cary, NC, USA). Differences across treatment groups will be assessed using ANOVA where treatment group was the main factor and BMI (at baseline), gender, and baseline measurement were covariates. Changes in measured variables from baseline to the end of the study within each group will also be assessed after correcting for BMI (at baseline), gender, and baseline values. Stool bacterial data will be log2 transformed for the statistics and then converted back to the numerical values for data presentation. Correlations will be analyzed using Pearson's method. Changes in OTU abundances will be determined using DESeq2 (ver. 1.14) [33] in the R Bioconductor package (<http://www.bioconductor.org>) (ver. 3.1.2). P-values for stool bacterial data and correlations will be corrected using the false discovery rate procedure. P-values for other comparisons will be adjusted using Tukey's procedure. Adjusted  $p < 0.05$  will be considered significant.

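### If the screening diet questionnaire is also the intake baseline, as the protocol most naturally reads, within-arm intake change is expected to be biased upwards in every arm, control included

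*Protocol*

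**What the plan says.** **Screening.** Under Methods and Procedures, item 2, "potential subjects will complete a diet history questionnaire online as part of the screening process". On the low-intake criterion the inclusion list says "this will be assessed by the diet history questionnaire and should be <1 serving/d for each food group".

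**Number and timing.** The same list contains "Be willing to complete 2 diet history questionnaires online", and Description of Participants, item 5, gives the same count. Methods and Procedures, item 3, says of the sampling sessions and the diet history: "Each subject will complete these sessions at the beginning and the end of the study". Its time budget ("Total estimated time for participation in this study is 6 hours over the course of 5 weeks") includes "two 60 minute diet history questionnaires". The visit schedule names no separate baseline questionnaire.

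**Other intake record.** "The food diary requires writing down all of the fruits, vegetables, and whole grain products consumed everyday" (Methods and Procedures, item 2). The diary plays no part in eligibility.

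**Analysis.** The SAP compares groups by ANOVA with baseline BMI, gender and the baseline measurement as covariates. It adds: "Changes in measured variables from baseline to the end of the study within each group will also be assessed", with the same three corrections. It does not name dietary intake as an outcome; intake could enter only as one of the measured variables.

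**The concern.** A diet questionnaire measures usual intake with error. People admitted because their reading fell below 1 serving/d include some whose reading was low by chance. When they are measured again, the average moves back up although nobody has changed what they eat. If the screening reading also serves as baseline, this movement is counted as change.

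The interpretation of intake is what is at stake. The control arm adds nothing to its normal diet, so an apparent rise there could be misread as controls taking up the test foods. In the two diet arms the change from screening would be inflated by a like amount. A test of within-arm change cannot separate this artefact from a real change.

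**Working it through.** **1. Is the screening questionnaire one of the two?** Items in the time budget: six 20-minute visits, two 30-minute clinical visits, two 60-minute questionnaires and 60 minutes of records.

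6×20 + 2×30 + 2×60 + 60 = 360 min = 6 h, which is the stated total. A third questionnaire, if counted, would give 420 min = 7 h. The tally fits two in all, but does not prove it (see the objection).

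**2. Expected rise with no true change.** Let X1 be the screening reading and X2 the end reading, each with mean μ and SD σ, and correlation (reliability) ρ. Subjects enter if X1 < c = 1. Put z = (c − μ)/σ and λ = φ(z)/Φ(z). In a normal model:

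- mean baseline = μ − σλ
- mean end reading = μ − ρσλ
- spurious rise = (1 − ρ)σλ
- variance of change = (1 − ρ)²σ²(1 − zλ − λ²) + σ²(1 − ρ²)

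The cut-off is the protocol's. The values of μ, σ and ρ are **assumptions**; neither document gives them. With μ = 1.0, σ = 0.8, ρ = 0.5: z = 0, λ = 0.798, baseline = 1.0 − 0.638 = 0.36, rise = 0.5 × 0.638 = 0.32, SD of change = 0.73. With 17 controls (the SAP's 52 divided by 3), the noncentrality is (0.319/0.734) × √17 = 1.79. The chance of a significant rise (two-sided 0.05, no multiplicity adjustment) is then 39%, against a nominal 2.5% in that direction. At μ = 1.5 and ρ = 0.5 the rise is 0.49 and the chance 76%.

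**3. A skewed model with milder cases.** The normal model allows negative servings, so the check was repeated with lognormal intake: log-SD s = 0.8, m = ln(median), z = −m/s. The mean baseline is exp(m + s²/2)·Φ(z − s)/Φ(z). The mean end reading is the same with ρs in place of s inside Φ. For median 1.0 and ρ = 0.5: 1.377 × 0.212/0.5 = 0.58 and 1.377 × 0.345/0.5 = 0.95, a rise of 0.37.

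Rise in servings/d per food group, with the simulated chance of a significant rise in 17 controls (paired t-test on log intake):

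| Assumed median | ρ = 0.5 | ρ = 0.7 | ρ = 0.9 |
|---|---|---|---|
| 0.7 | +0.22; 20% | +0.13; 13% | +0.04; 7% |
| 1.0 | +0.37; 39% | +0.21; 24% | +0.07; 11% |
| 1.5 | +0.58; 69% | +0.32; 45% | +0.10; 18% |

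With 40 per arm (the protocol's 120 divided by 3) the chance is 12% to 97%. A larger sample makes the false signal more likely, not less.

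**4. Does the baseline covariate remove it?** Within one arm, regressing change on the baseline value centred at its mean leaves the intercept equal to the arm's mean change, which still contains (1 − ρ)σλ. Between arms the same shift sits in each arm and cancels. In simulation with three arms of 17, the baseline-adjusted comparison kept its type I error at 4.2% to 5.4%.

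**5. A baseline not used for selection.** With a separate baseline reading whose errors are independent of screening, the mean spurious change was −0.001 to +0.002 serving/d in all nine settings.

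**The case against.** **The double use is not stated.** No sentence says that the screening questionnaire is the baseline. The six hours are spread over 5 weeks, which matches weeks −1 to 4, and the Compensation section pays for the screening questionnaire separately. Two further questionnaires on study remain possible. This stands: the double use is a well-supported inference that the protocol should confirm or correct.

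**Intake change may not be tested.** The SAP never names intake, and the protocol already has a daily diary and daily tracking of test foods, which are natural adherence records. This also stands; the point is conditional on the general within-group wording being applied to questionnaire intake.

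**The size is assumed.** It is. At reliability 0.9 the rise is at most 0.10 and could easily go unnoticed in an arm of 17. The normal model puts about 21% (mean 1.0) or 11% (mean 1.5) of admitted readings below zero, although the skewed model gives rises of similar size. The probabilities are for a simple unadjusted test, not the planned covariate-adjusted and Tukey-corrected one. The range therefore has to include the mild cases.

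**Stronger readings that fail.** A reader might infer that adherence itself is overstated. Selection makes the baseline reading too low; it does not inflate the end reading, so intake judged against the assigned 3 or 5 servings is unaffected. A reader might also infer that the comparison of arms or the biomarker results are compromised. The adjusted between-arm contrast is sound if the arms are exchangeable, and no blood or stool marker was used to select on intake. Exchangeability is itself a condition, because neither document describes how subjects are assigned.

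**Conclusion.** The concern holds conditionally and is minor. If the two questionnaires include the screening one, reported intake is expected to rise from baseline in all three arms with no change in diet, and a within-arm test of that change is biased. Adjusting for baseline does not cure it. Over the assumed inputs (centre 0.7 to 1.5 servings/d, SD 0.8 on the natural or log scale, reliability 0.5 to 0.9), the rise is about 0.04 to 0.6 serving/d per food group. The chance of a falsely significant rise in 17 controls is roughly 7% to 76%, taking both models together.

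This is an expectation, not a prediction that each arm will visibly rise. It is confined to within-arm change in questionnaire intake.

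**What to change.** - **Protocol:** state whether the two questionnaires include the screening one.
- **SAP, questionnaire:** analyse questionnaire intake only as a baseline-adjusted comparison between arms at the end of the study, and drop within-arm tests of change from the screening questionnaire.
- **SAP, diary:** for within-arm change in fruits, vegetables and whole grains, use the daily food diary, with the week −1 to 0 diary as baseline. The sponsor must first confirm that all arms, control included, keep it before intervention foods begin. The visit schedule makes this likely but does not say so.

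The cost is a few sentences and the analysis of records that the protocol already calls for, provided that diary week exists in every arm. There is a small downside: the diary covers only these food groups, so within-arm change in other nutrients would go untested or would still rest on the screening questionnaire.
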